#### 3.2 Discussion of Study Design

## 3.2.1 Rationale for the Dose and Dosage of the Study Drug

In the overseas Phase 1 study (Study CP0001), quizartinib was administered intermittently at doses of 12 mg/day to 450 mg/day (14 days on treatment, followed by 14 days of rest) and at doses of 200 mg/day and 300 mg/day for 28 consecutive days in 76 AML patients, and the maximum tolerated dose of quizartinib was 200 mg/day that was administered for 28 consecutive days. In the overseas Phase 2 study (Study AC220-002), quizartinib was administered at a dose of 200 mg/day for 28 consecutive days in 333 AML patients, and Grade 3 QTc prolongation was reported in 42% of the patients. The incidence of QTc prolongation tended to be higher in female than male patients, and the dose of quizartinib was reduced to 135 mg/day in male patients and 90 mg/day in female patients during the course of Study AC220-002. TdP associated with Grade 4 QTc prolongation occurred in one female patient receiving consecutive-day treatment with quizartinib at a dose of 90 mg/day concomitantly with a strong CYP3A4 inhibitor. Therefore, in the overseas Phase 2b study (Study 2689-CL-2004), quizartinib was administered at 30 mg/day or 60 mg/day for 28 consecutive days to assess the safety and efficacy of quizartinib at lower doses. As a result, the incidence of QTc prolongation significantly decreased in the 30 mg and 60 mg groups compared with the higher dose groups (90 mg to 200 mg) established in Study AC220-002, which indicated that the potential risk of QTc prolongation was dose-dependent. The incidence of increased QTc interval to longer than 500 ms was 5% and 3% in the 30 mg and 60 mg groups, respectively, while the incidence of change in QTc interval of longer than 60 ms from baseline was 3% and 19%, respectively (Table 1.2-1). It was also clarified that the CRc rate in the 30 mg and 60 mg groups was equivalent to that in the high dose groups (90 mg to 200 mg) in Study AC220-002 (Table 1.2-2).

Increased QT/QTc interval to longer than 500 ms and an increase of longer than 60 ms in QT/QTc interval from baseline are important changes to decide whether to conduct a clinical study or not. According to the results of Study 2689-CL-2004, the incidence of increased QTc interval to longer than 500 ms was as low as 5% or less in the 30 mg and 60 mg groups, and the incidence of a longer than 60 ms increase in QTc interval from baseline was lower in the 30 mg and 60 mg groups than in the 90 mg or higher dose groups. Based on these data, it was considered that quizartinib is tolerated at doses of 30 mg and 60 mg, and the initial dose of 30 mg was chosen in this study. The rationale for setting 20 mg/day as the initial dose of quizartinib for patients concomitantly using strong CYP inhibitors is shown below.

In a drug-drug interaction study in healthy adult subjects, ketoconazole (strong CYP3A4 inhibitor) or fluconazole (moderate CYP3A4 inhibitor) was administered as multiple doses, followed by quizartinib as a single dose; concomitant treatment with ketoconazole or fluconazole resulted in 1.17-fold or 1.11-fold Cmax, respectively, and 1.94-fold or 1.20-fold AUCinf, respectively, compared with quizartinib monotherapy. Based on this result, it was estimated that the steady-state plasma quizartinib concentration following administration of multiple-dose quizartinib concomitantly with ketoconazole or fluconazole would increase by 1.86-fold or 1.21-fold, respectively, for Cmax and by 1.96-fold or 1.21-fold, respectively, for AUC0.24, compared with quizartinib monotherapy. This result indicates that exposure to quizartinib nearly doubles when quizartinib is concomitantly used with strong CYP3A4 inhibitors, and it was therefore considered appropriate to administer quizartinib at a dose of 20 mg/day, which is about half the dose, in the presence of strong CYP inhibitors. Meanwhile, exposure to quizartinib concomitantly used with moderate CYP3A4 inhibitors is limited, and it was therefore considered unnecessary to reduce the dose of quizartinib in the presence of moderate CYP3A4 inhibitors. The initial dose of quizartinib in Study AC220-007 was set at 30 mg/day (20 mg/day in the presence of strong CYP3A4 inhibitors) for the same reason.

### 3.2.2 Rationale for the Method of Dose Increase of the Study Drug

In Study 2689-CL-2004, the CRc rate at the final analysis was 47% in both the 30 mg and 60 mg groups; however, CRc was not achieved in 63% (24/38 patients) of the patients in the 30 mg group after the end of Cycle 1, and the dose was increased to 60 mg accordingly. Meanwhile, the proportion of patients in the 60 mg group who did not achieve CRc after the end of Cycle 1 and for whom the dose was increased to 90 mg was 19% (7/36 patients). Although these data are limited, a higher tendency for efficacy

was observed in the 60 mg group than the 30 mg group when it was measured by other endpoints such as the transplantation rate, PR rate, duration of CRc, and median OS, and the 60-mg dose is thus likely to be superior to the 30-mg dose in terms of efficacy. When the relationship between exposure to AC220 and its active metabolite AC886 and the efficacy on Day 15 of Cycle 1 was compared between the two dose groups, no significant correlation between the 30 mg and 60 mg groups was observed in the CRc rate after the end of Cycle 1, or AUC0 24h of AC220, AUC0 24h of AC886, or the sum of AUC0 24h of AC220 and AC886 on Day 15 of Cycle 1, which suggests that there is no difference in exposure between these dose groups at the end of Cycle 1. Accordingly, it is considered that there is no great difference in efficacy when quizartinib is administered at an initial dose of 30 mg and increased to 60 mg on Day 16 of Cycle 1 and when quizartinib is administered at an initial dose of 60 mg.

In addition, when the relationship between drug concentrations and QTc interval was evaluated using the data from Study 2689-CL-2004, a linear relationship between prolongation of QTc interval and plasma AC220 concentrations was found. The half-life of AC220 was approximately 3 days, and quizartinib exposure reached a steady state on Day 15 of Cycle 1 in both the 30 mg and 60 mg groups. Therefore, prolongation of QTc interval caused by AC220 was estimated to reach a peak on Day 15 of Cycle 1. Data from Study 2689-CL-2004 did not show any significant correlation between plasma AC886 concentrations and prolongation of QTc interval. In view of these data, it was considered possible to increase the dose of quizartinib from 30 mg to 60 mg on Day 16 of Cycle 1 or later based on the assessment on Day 15 of Cycle 1, when the plasma quizartinib concentration reaches a steady state, in accordance with "5.2.4.3 Criteria for Dose Increase of the Study Drug."

#### 3.2.3 Rationale for Sample Size

Refer to Section "11.5 Determination of Sample Size."

#### 4. STUDY POPULATION

Prior to assessment of eligibility for enrollment in the study, patients must sign the informed consent form (ICF) provided by the study center, and date it. patients who meet all of the following inclusion criteria and do not fit any of the exclusion criteria and who provide written informed consent of their free will are eligible for the study.

#### 4.1 Inclusion Criteria

Patients must satisfy all of the following criteria to be included in the study:

- 1) Provision of written informed consent for participation in the study.
- 2) Patients aged 20 years or older when consent is obtained.
- 3) Primary AML patients or AML patients with a history of myelodysplastic syndrome (MDS).
- 4) AML patients who have first relapsed within 6 months after achieving remission with initial remission induction therapy or those who are refractory to all therapies given prior to the start of the study and failed to achieve remission. The initial remission induction therapy must be a regimen containing at least 1 cycle of standard-dose treatment with anthracyclines or mitoxantrone. It is not taken into consideration whether they have HSCT or not.
  - Definition of refractory to treatment
    - Patients who have less than 50% reduction in bone marrow blasts and have failed to achieve CR, CRp, or CRi after 1 cycle of treatment.
    - Patients who have failed to achieve CR, CRp, or CRi after 2 cycles of treatment.
  - Definition of first relapse (within 6 months after achieving remission)
    - Patients who have achieved CR, CRp, or CRi after initial remission induction therapy and have relapsed within 6 months. It is not taken into consideration whether they have received consolidation therapy, maintenance therapy, or HSCT or not.
    - The duration of remission is defined as the day of the bone marrow test when CR, CRp, or CRi was confirmed or the day of HSCT to the day of the bone marrow test when relapse was confirmed or the day of reappearance of leukemic blasts in the peripheral blood.
- \*A specimen for the FLT3-ITD mutation test will be submitted to Navigate BioPharma Services, Inc. (Navigate BioPharma), the central laboratory, to test mutations in the FLT3-ITD gene. However, patients who have been confirmed to be FLT3-ITD positive in the FLT3-ITD testing previously performed at another testing company or the central laboratory, SRL Inc. (SRL), may be assessed for eligibility for the study without waiting for the result of measurement at Navigate BioPharma.
- 6) Eastern Cooperative Oncology Group performance status (ECOG PS) score 0 to 2

- (refer to "Appendix 2").
- 7) Patients in whom the intervals listed below can be achieved between the last dose or application of prior therapy and the first dose of the study drug in the study:
  - Cytotoxic drugs (excluding hydroxycarbamide used for the purpose of controlling the increase in white blood cells): 2 weeks
  - Non-cytotoxic drugs: at least  $5 \times$  the half-life of the drug
- 8) Laboratory test results obtained within 14 days before registration meet all of the following requirements:

Laboratory Parameter	Requirement
AST	≤ 2.5 times the upper limit of the institutional reference range
ALT	$\leq$ 2.5 times the upper limit of the institutional reference range
Total bilirubin	$\leq$ 1.5 times the upper limit of the institutional reference range
Serum creatinine	$\leq$ 1.5 times the upper limit of the institutional reference range (or estimated glomerular filtration rate [eGFR]* $\geq$ 25 mL/min/1.73 m  )
Serum K	Within the institutional reference range**
Serum Mg	Within the institutional reference range**
Serum Ca (corrected for albumin)	Within the institutional reference range**

\* eGFR (mL/min/1.73 m^2)  $194 \times \text{serum creatinine}^{1.094} \times \text{age}^{0.287} (\times 0.739 \text{ for females})$ 

9) Patients who can receive quizartinib orally.

#### Rationale

- 1), 9) To ensure the eligibility as a study patient and for ethical considerations.
- 2) Twenty is considered the minimum age for patients to be able to provide appropriate informed consent based on their own decision.
- 3) to 6) To appropriately evaluate the efficacy of quizartinib in Japanese patients with FLT3-ITD positive relapsed or refractory AML.
- 7) To ensure that patients are in a stable physiological condition at the time of registration based on the "Guidelines for the Clinical Evaluation of Anticancer Drugs."
- 8) To ensure that organ functions allowing the appropriate evaluation of patient safety have been maintained based on the "Guidelines for the Clinical Evaluation of Anticancer Drugs.)"

\*\* Patients with electrolytes outside the institutional reference range will be eligible if these values are corrected upon retesting following any necessary supplementation.

#### 4.2 Exclusion Criteria

Patients who meet any of the following criteria will be disqualified from entering the study:

- 1) Diagnosis of acute promyelocytic leukemia.
- 2) Patients who developed AML in association with prior chemotherapy or radiotherapy given to treat another malignant tumor than AML (patients with treatment-related AML). However, this shall not apply to patients with a history of MDS.
- 3) History of malignant tumor within 5 years before registration. However, participation of the following patients in the study is allowed.
  - Curatively treated skin cancer other than malignant melanoma, carcinoma in situ, or cervical carcinoma in situ (The time to onset of AML is not considered when the standard therapy has been completed.)
  - Prostate cancer without local recurrence or progression (any of the cases in which hormonal therapy has been initiated, the tumor has been surgically removed, or the lesion has disappeared with radiotherapy)
- 4) Persistent, symptomatic Grade 2 or more severe non-hematological toxicity (excluding alopecia) from prior therapy.
- 5) GVHD that is clinically significant or requiring treatment, those who need to start treatment for GVHD, those requiring intensified treatment for GVHD within 21 days before registration, or those with Grade 2 or more severe clinically significant or irreversible non-hematological toxicity related to HSCT.
- 6) History of or current symptomatic central nervous system involvement with clinical symptoms.
- 7) Disseminated intravascular coagulation, or other clinically significant coagulation abnormalities.
- 8) Prior treatment with quizartinib or prior participation in any clinical study of quizartinib.
- 9) Prior treatment with other FLT3 inhibitors (sorafenib or other FLT3 inhibitors under development) (This does not include midostaurin.)
- 10) Extensive surgery within 28 days before registration.
- 11) Radiation therapy within 28 days before registration.
- 12) History of or current cardiovascular disease as specified below:
  - QTcF interval of 450 ms or longer, determined as the average of three central ECG measurements taken within 14 days before registration
  - Heart rate of 50 beats/min or lower, determined as the average of three central

- ECG measurements taken within 14 days before registration (excluding patients with a cardiac pacemaker)
- Previous, current, or suspected long QT syndrome, or a family history of congenital long QT syndrome
- History of life-threatening ventricular arrhythmia, such as ventricular tachycardia, ventricular fibrillation, or TdP
- Second or third degree heart block
   (This shall not apply to patients who have second or third degree heart block, but who have a cardiac pacemaker and have never experienced syncope or arrhythmia before.)
- History of myocardial infarction within 6 months before registration
- History of uncontrolled angina pectoris within 6 months before registration
- Class III or more severe congestive heart failure according to "Appendix 3 New York Heart Association (NYHA) Functional Classification"
- Left ventricular ejection fraction (LVEF) below 45% or the lower limit of the institutional reference range
- Uncontrolled hypertension
- Complete left or right bundle branch block
- 13) Active infection that is not well controlled with antibacterial, antifungal, or antiviral therapy.
- 14) Active liver disease (hepatitis B, hepatitis C, etc.)
- 15) Tested positive for human immunodeficiency virus (HIV) antibody within 120 days before registration.
- 16) Women of childbearing potential, or their male partners who are unable or unwilling to practice appropriate contraception using effective contraceptive methods (eg, barrier contraceptives combined with spermicides, intrauterine device) for the entire study period and 3 months after the last dose of the study drug.
  - Women of non-childbearing potential (postmenopausal women with no menses for at least 2 years and women who have undergone hysterectomy etc. at least 1 month before registration) may be registered in the study.
  - Male patients may not donate their sperm during the period from 14 days before registration to 105 days after the last dose of the study drug. Female patients may not donate their eggs during the period from 14 days before registration to 12 weeks after the last dose of the study drug.
- 17) Women found to be pregnant by a pregnancy test performed within 14 days before

- registration.
- 18) Women who may need to breastfeed during the study period and for 25 days after the last dose of the study drug.
- 19) Patients who are otherwise considered ineligible for the study in the opinion of the investigators.

#### Rationale

- 1) to 18) Established to appropriately evaluate the efficacy of quizartinib, taking the safety of the use of quizartinib into consideration.
- 16) to 18) Established because effects of quizartinib on the fetus and nursing babies cannot be ruled out. Breastfeeding women, independent of whether they interrupt breastfeeding or not, are not eligible for participation in the study.
- 19) Established so that the investigators can determine the eligibility for participation in the study from a comprehensive standpoint with careful consideration for patient safety.

#### 5. STUDY TREATMENT

## 5.1 Assigning Patients to Treatments and Blinding

#### **5.1.1** Treatment Groups

This is a single-arm study.

## **5.1.2** Method of Treatment Allocation

This is a single-arm study and randomization will therefore not be performed. Registration of patients will be performed via fax. The procedure for patient registration is shown in Figure 5-1.

After obtaining written informed consent from each patient, the investigators will assign a subject identification code to the patient. If the above-stated patient is assessed to be eligible for the study, the investigators will enter the necessary information on the patient in the subject registration form and send it to the sponsor by fax.

The sponsor will check the eligibility of the patient in the light of the inclusion and exclusion criteria for the study based on the entries in the received subject registration form. If there are any questions about the entries in the registration form, the sponsor should immediately contact the investigators to make inquiries. When the sponsor determines that the patient is eligible for the study, the sponsor will register the patient and assign the subject number.

The sponsor will immediately fax the registration confirmation form together with the result of the eligibility assessment to the investigator; the confirmation form should include the date of registration, subject number, and dose of the study drug for patients assessed to be eligible, and the fact that the patient is not eligible and the reason for patients assessed to be ineligible. The investigators will explain the reason for ineligibility to patients assessed to be ineligible by the sponsor.

A	dress for sending the subject registration form	
	(the sponsor's address)	
,	Vorking hours: Monday to Friday, 9:00 to 17:30	
(c	osed on Saturdays, Sundays, and public holidays)	
	FAX:	
	TEL:	

The investigators may not dispense the study drug to a patient until the patient is registered.

If any patient provides informed consent but is not registered, the investigators will describe the reason why the patient is not registered in the medical record. The patient will not be included in the number of patients enrolled in the study.

Even if a patient is considered ineligible by the investigators at the time of eligibility check after providing informed consent, and the subject registration form of the patient is not faxed to the sponsor, if the investigators later confirms that the patient meets the eligibility criteria, the investigators may again obtain consent for participation in the study from the patient and fax the subject registration form to the sponsor.

[figure not shown]

Figure 5-1 Patient Registration Procedure

### 5.1.3 Blinding

This is an open-label study.

### **5.1.4** Emergency Unblinding Procedure

Not applicable

## 5.2 Study Drug

### 5.2.1 Description

For the details of the study drug and its handling, see the "Investigator's Brochure" and "Study Drug Management Procedures."

1) Investigational substance code: AC220

2) Generic name (r-INN): Quizartinib

3) Content and dosage form: White film-coated tablets, each of which contains

20 mg AC220, or yellow film-coated tablets, each

of which contains 30 mg AC220.

4) Lot number:

Lot numbers are listed in the "Study Drug Management Procedures."

## 5.2.2 Labeling and Packaging

The packaging form and information displayed on the label of the study drug will be provided in the "Study Drug Management Procedures."

Thirty study drug tablets are packaged in a plastic bottle (for 1 patient).

The information displayed on the label is shown in "Table 5.2-1 Information Displayed on the Study Drug Label."

Table 5.2-1 Information Displayed on the Study Drug Label

Statement, "For clinical study"
Name of the study drug
Protocol number
Lot number of the study drug
Storage conditions
Statement, "Do not discard but store any unused study drug tablets; they will be collected later."
Name of the sponsor
Address of the sponsor

### 5.2.3 Preparation

All study drugs will be supplied as tablets that need no further preparation at the study centers.

#### 5.2.4 Administration

# 5.2.4.1 Dose of the Study Drug

Quizartinib will be administered at an initial dose of 30 mg/day. For patients receiving strong CYP3A4 inhibitors, an initial dose of 20 mg/day will be used. Subsequently, whether or not to increase the initial dose of 30 mg/day to 60 mg/day or 20 mg/day to 30 mg/day will be determined on Day 16 of Cycle 1 and Day 1 of Cycle 2 (or thereafter) in accordance with "5.2.4.3 Criteria for Dose Increase of the Study Drug." If patients who achieve CR, CRp, or CRi after the start of treatment with the study drug and then subsequently relapse meet "5.2.4.3 Criteria for Dose Increase of the Study Drug," the dose of quizartinib may be increased in the same manner.

The dose of the study drug will be reduced in accordance with each of the criteria for dose reduction given in "5.4 Dose Interruptions and Reductions." If the dose is reduced due to QTcF prolongation, treatment for QTcF prolongation will be given in accordance

with "9.10.2 Measures Taken in Case of QTcF Prolongation."

In principle, central ECG assessment results will be used to make a decision on dose increase or reduction of the study drug. If it is necessary to urgently confirm the central assessment results on Day 15 of Cycle 1 or Day 1 of Cycle 2, etc., the study center should contact the Central ECG Reading Center and request immediate assessment (within 24 hours).

### **5.2.4.2** Regimen

Quizartinib will be orally administered once daily every morning. Treatment with quizartinib will be administered in 28-day cycles and continued until "5.7.1 Discontinuation Criteria for Treatment with the Study Drug" are met. The first dose of the study drug will be started, in principle, within 7 days of registration. If treatment with the study drug is started more than 7 days after registration, it should be confirmed again that the patient meets the eligibility criteria before the start of the first dose of the study drug.

If a patient vomits after taking a dose of the study drug, a replacement dose may not be given on the same day.

A patient who did not take the study drug at the usual hour of dosing (eg, forgot to take the dose) will be allowed to take the missed dose within 10 hours after the usual hour of dosing (for example, if the patient usually takes the drug at 7:00 or 8:00, he/she may take it by 18:00). In this case, the next dose of the study drug on the following day should be taken at least 12 hours after the time when the last dose was taken. If the patient does not take the missed dose by 10 hours after the usual hour of dosing, he/she should not take the study drug on that day and resume taking the drug on the following day. The patient may not take two doses at once on the day when the drug is resumed.

## 5.2.4.3 Criteria for Dose Increase of the Study Drug

If the patient's condition satisfies the following criteria on Day 16 of Cycle 1 or Day 1 of Cycle 2 (or thereafter), the dose of quizartinib will be increased according to Table 5.2-2. A 12-lead ECG will be measured at least once weekly for the first 2 weeks after a dose increase to confirm the presence or absence of QTcF prolongation after the dose increase. When doing this, triplicate ECG recordings will be obtained. The dose of quizartinib should not exceed 60 mg/day throughout the study period (30 mg/day for patients concomitantly using strong CYP3A4 inhibitors).

Table 5.2-2 Method of Dose Increase of Quizartinib

Dose	One level Increased Dose
20 mg/day	30 mg/day
30 mg/day	60 mg/day
60 mg/day	No dose increase

### Assessment criteria for dose increase on Day 16 of Cycle 1

Patients not concomitantly using strong CYP3A4 inhibitors:

The dose of quizartinib will be increased to 60 mg/day if all QTcF data (determined as the average of three measurements) taken by Day 15 of Cycle 1 are 450 ms or shorter.

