- 17) Women found to be pregnant by a pregnancy test performed within 14 days before registration.
- 18) Women who may need to breastfeed during the study period and for 25 days after the last dose of the study drug.
- 19) Patients who are otherwise considered ineligible for the study in the opinion of the investigators (investigator or subinvestigator).

Dosage form, dose and route of administration:

<Dosage form>

White film-coated tablets, each of which contains 20 mg AC220, or yellow film-coated tablets, each of which contains 30 mg AC220.

<Regimen>

Quizartinib will be administered at an initial dose of 30 mg/day. For patients receiving strong cytochrome P450 (CYP) 3A4 inhibitors, an initial dose of 20 mg/day will be used. Quizartinib will be orally administered once daily every morning. Treatment with quizartinib will be administered in

28-day cycles and continued until the withdrawal criteria are met.

If a patient vomits after taking a dose of the study drug, a replacement dose may not be given on the same day. A patient who did not take the study drug at the usual hour of dosing (eg, forgot to take the dose) will be allowed to take the missed dose within 10 hours after the usual hour of dosing (for example, if the patient usually takes the drug at 7:00 or 8:00, he/she may take it by 17:00 or 18:00). In this case, the next dose of the study drug on the following day should be taken at least 12 hours after the time when the last dose was taken. If the patient does not take the missed dose by 10 hours after the usual hour of dosing, he/she should not take the study drug on that day and resume taking the drug on the following day. The patient may not take two doses at once on the day when the drug is resumed.

<Criteria for dose increase of the study drug>

The dose of quizartinib will be increased in accordance with the following criteria. A 12-lead ECG will be measured at least once weekly for the first 2 weeks after a dose increase to confirm the presence or absence of QTcF prolongation after the dose increase. When doing this, triplicate ECG recordings will be obtained.

Assessment criteria for dose increase on Day 16 of Cycle 1
Patients not concomitantly using strong CYP3A4 inhibitors:
The dose of quizartinib will be increased to 60 mg/day if all
QTcF data (determined as the average of three measurements)
taken by Day 15 of Cycle 1 are 450 ms or shorter.

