# 5.4.4 If Concomitant Use of Strong CYP3A4 Inhibitors Is Started during the Study Period

If concomitant use of strong CYP3A4 inhibitors is started during the study period, the dose of quizartinib will be reduced by one level. If concomitant use of strong CYP3A4 inhibitors is discontinued, quizartinib may be administered at the dose used before dose reduction after a 7-day washout.

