#### 5.4.5 Dose Increase after Dose Reduction

The dose of quizartinib will be increased by one level at a time in patients whose dose has once been reduced. However, if the dose of quizartinib is reduced associated with

Grade 3 QTcF prolongation, the dose may not be increased. If the dose of quizartinib is reduced associated with Grade 2 QTcF prolongation, the dose may be increased to the dose before dose reduction if QTcF prolongation recovers to Grade 1 or less severe after treatment at a reduced dose for at least 28 days.

If the dose of quizartinib is reduced due to AEs, the dose must not be increased unless the concerned AE recovers to Grade 1 or less severe. If the dose of quizartinib is reduced because concomitant use of a strong CYP3A4 inhibitor is started during the study, quizartinib may be administered at the dose before dose reduction after a 7-day washout when the concomitant use of the strong CYP3A4 inhibitor is discontinued.

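### No washout is required before 60 mg/day when a patient who started at 20 mg/day on a strong CYP3A4 inhibitor later stops it

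*Combined protocol and SAP*

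**What the plan says.** Section 5.2.4.1 starts patients at 30 mg/day, or at 20 mg/day if they are taking a strong CYP3A4 inhibitor. It names two upward steps: "whether or not to increase the initial dose of 30 mg/day to 60 mg/day or 20 mg/day to 30 mg/day will be determined". The lead-in to Section 5.2.4.3 says that if the criteria are met "the dose of quizartinib will be increased according to Table 5.2-2". That table moves 20 to 30 and 30 to 60 mg/day. The ceiling is 60 mg/day, or "30 mg/day for patients concomitantly using strong CYP3A4 inhibitors".

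The Day 16 criteria then divide patients by whether they are using a strong inhibitor at that time, not by starting dose. For those not using one: "The dose of quizartinib will be increased to 60 mg/day if all QTcF data" up to Day 15 are at or below 450 ms. The Protocol Synopsis has the same sentence ("The dose of quizartinib will be increased to 60 mg/day if all") without the table. The criteria for Day 1 of Cycle 2 or later apply the same distinction between users and non-users when they name the target dose for relapsed patients.

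The washout is in Section 5.4.4. Its trigger is: "If concomitant use of strong CYP3A4 inhibitors is started during the study period, the dose of quizartinib will be reduced by one level". When that inhibitor is stopped, "quizartinib may be administered at the dose used before dose reduction after a 7-day washout". Section 5.4.5 repeats this for doses cut because an inhibitor was started during the study, and adds: "The dose of quizartinib will be increased by one level at a time in patients whose dose has once been reduced".

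**The concern.** The washout is tied to a return to the dose held before a reduction. A patient who entered on an inhibitor and started at 20 mg/day has no such earlier dose, so neither 5.4.4 nor 5.4.5 applies. On the day the inhibitor stops, the patient leaves the 30 mg/day ceiling and comes under the rules for non-users. If a decision point falls then, 60 mg/day is allowed at once.

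This is inconsistent with the plan's own approach. A patient cut from 60 to 30 mg/day for a newly started inhibitor must wait 7 days after stopping it before resuming 60 mg/day. A patient at 30 mg/day who had the inhibitor from the outset need not wait, although the residual inhibition could be the same.

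At stake is a short period of exposure above what the plan otherwise permits. Section 3.2.1 justifies the lower starting dose by the near doubling of exposure with a strong inhibitor, and Section 3.2.2 reports a linear relation between QTc prolongation and plasma quizartinib concentration.

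**Working it through.** The plan gives no figure for this situation, so there is none to reproduce. The check traces the rules and then sizes the exposure.

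**Rule trace.** The patient starts at 20 mg/day on an inhibitor and has never been dose-reduced.

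| Situation | One-level reading (lead-in, Table 5.2-2, 5.2.4.1) | Day 16 sentence read alone | Washout required |
|---|---|---|---|
| Inhibitor stopped just before Day 16 | 30 mg/day | 60 mg/day | None |
| Raised to 30 mg/day on Day 16, inhibitor stopped just before Day 1 of Cycle 2 or later | 60 mg/day | Not applicable | None |

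Under the one-level reading, a patient who stops before Day 16 reaches 60 mg/day no sooner than Day 1 of Cycle 2, that is 29 − 16 = 13 days later, so 7 days have passed anyway. The gap therefore concerns an inhibitor stopped within 7 days before an increase at Day 1 of Cycle 2 or later.

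**Inputs.**
- Half-life of about 3 days (Section 1.2.1.2.5).
- Estimated steady-state AUC ratio of 1.96 with ketoconazole (Section 3.2.1).
- Assumptions: one compartment, constant volume, dose proportionality down to 20 mg/day (the protocol reports it for 30 to 90 mg), and continuous input.

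**Formula.** Let E be exposure in mg/day-equivalents, so that 60 mg/day without an inhibitor settles at 60. With D the daily dose and F the inhibition factor (1.96 or 1), E moves towards D × F at rate k/F, where k = ln 2 / 3 = 0.2310 per day. Under full inhibition the rate is 0.2310 / 1.96 = 0.1179 per day.

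**Cycle 2 route** (15 days at 20 mg/day, 13 days at 30 mg/day, both with the inhibitor, then 60 mg/day):
- End of 20 mg/day: 39.2 × (1 − e^(−0.1179×15)) = 39.2 × 0.829 = 32.5.
- End of 30 mg/day: 58.8 − (58.8 − 32.5) × e^(−0.1179×13) = 58.8 − 26.3 × 0.216 = 53.1.
- At 60 mg/day with full inhibition for h more days: E = 117.6 − (117.6 − 53.1) × e^(−0.1179h).
  - h = 0: E rises from 53.1 towards 60, with no excess.
  - h = 3: 117.6 − 64.5 × 0.702 = 72.3.
  - h = 7: 117.6 − 64.5 × 0.438 = 89.3.
- If F instead falls linearly from 1.96 to 1 over 7 days, numerical integration gives a peak of about 74.

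Relative to the permitted 60, the peaks for 3 days, 7 days and linear waning are 72/60 = 1.20, 89/60 = 1.48 and 74/60 = 1.23.

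**Day 16 route** (only if that sentence is read alone; 60 mg/day from E = 32.5):
- h = 3: 117.6 − 85.1 × 0.702 = 57.8, then towards 60, so no excess.
- h = 7: 117.6 − 85.1 × 0.438 = 80.3.

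**With a 7-day wait at 30 mg/day** (Cycle 2 route, inhibition full for all 7 days): 58.8 − (58.8 − 53.1) × 0.438 = 56.3. The later move to 60 mg/day, now uninhibited, approaches 60 from below. The wait removes the excess if inhibition lasts no more than 7 days.

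**The case against.** The strongest reply is that Section 5.2.4.3 already gives a single dose. The lead-in sends every increase through Table 5.2-2, whose only step from 20 mg/day is to 30, and 5.2.4.1 names no step from 20 to 60. On that view the Day 16 sentence says when to increase and the lead-in says by how much. This stands. A reader might infer that the protocol prescribes two different doses on Day 16 for the same patient. That needs the sentence to be read apart from its own lead-in, so the one-level wording is only a clarification. It does not close the washout gap, which remains under the one-level reading.

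Second, the group is small. Section 5.6.2.2 allows strong inhibitors but advises against them. The patient must stop the inhibitor within days of a decision point and meet the criteria for an increase. This also stands, and the documents do not allow the number to be estimated.

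Third, the excess depends on inhibition persisting after the drug is stopped, and the documents give no offset time for any inhibitor. With immediate offset there is no excess. The only anchor is the sponsor's own 7 days.

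Fourth, safeguards apply throughout: triplicate ECGs at least weekly for two weeks after an increase, central reading in principle, and the QTcF reduction and interruption rules. On the Cycle 2 route the patient must also show a QTcF rise of no more than 60 ms, at a modelled exposure of about 53. These limit the consequence but do not replace the missing wait.

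**Conclusion.** The gap is real and narrow. The washout does not reach a strong inhibitor already in use at study start, so 60 mg/day may follow its withdrawal at once: at Day 1 of Cycle 2 or later on the governing reading, and on Day 16 only if that sentence is taken alone. The modelled peak on the Cycle 2 route is about 72 to 89 mg/day-equivalents with 3 to 7 further days of full inhibition, or about 74 with linear waning over 7 days, against 60. These figures rest on a one-compartment model, the ketoconazole ratio and an assumed offset.

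Two stronger inferences should not be drawn. The value of about 118 (60 × 1.96) is reached only if inhibition never wanes, so it is not a forecast. The torsades case in Section 1.2.1.2.2 occurred at 90 mg/day with a strong inhibitor, about 90 × 1.96 = 176 equivalents and roughly twice the highest peak above (176/89 = 2.0), so it does not show what would happen here.

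The primary analysis is unaffected: Section 11.1 treats all patients as one dose group whatever the dose changes. Severity is at the low end of minor.

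**What to change.** In Sections 5.2.4.3 and 5.4.4, require at least 7 days since the last dose of any strong CYP3A4 inhibitor, including one in use at study start, before any dose above 30 mg/day. As a clarification, add to the Day 16 sentence and to the Protocol Synopsis that the increase is by one level according to Table 5.2-2.

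This is a wording amendment and a note to sites, with no added patients, visits or tests. The price is a later move to 60 mg/day, which Section 3.2.2 regards as probably the more effective dose. The delay is about 7 days where the increase may be decided on Day 1 of Cycle 2 or thereafter. For a patient who would otherwise have been raised to 60 mg/day on Day 16, it is up to about 13 days, to Day 1 of Cycle 2. Allowing 20 to 60 mg/day directly after the washout would not reliably shorten this: if the inhibitor stops on Days 10 to 15, the 7 days end after Day 16 and the next decision point is still Day 1 of Cycle 2.
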